4.2. Study Design

This is a global, multicenter, randomized (2:1), open-label, Phase 3 study comparing selpercatinib (treatment Arm A) to physicians' choice of cabozantinib or vandetanib (treatment Arm B) in patients with progressive, advanced, kinase inhibitor naïve, rearranged during transfection (RET)-mutant medullary thyroid cancer (MTC).

Patients will be randomized in a 2:1 ratio to selpercatinib or physician's choice of cabozantinib or vandetanib.

Patients will be stratified based on:

- RET mutation: M918T vs. other
- Intended treatment if randomized to control arm: cabozantinib vs. vandetanib

Approximately 250 patients will be initially enrolled in the study. A sample size re-estimation based on comparative data will be conducted at the interim efficacy analysis. The total number of patients could be increased from the initially planned 250 up to a maximum of approximately 400 depending on the results of the interim efficacy analysis. The total study duration will be capped at 6 years from the first patient visit.

Patients with histologically confirmed, unresectable, locally advanced, or metastatic MTC who have not received previous treatment with a kinase inhibitor are eligible. Patients are required to have radiologic progressive disease (PD) per Response Evaluation Criteria in Solid Tumors, version 1.1 (RECIST 1.1, Eisenhauer et al. 2009) at screening compared with an image obtained within the prior 14 months. Patients are also required to have a documented RET mutation in tumor or germline deoxyribonucleic acid (DNA) identified through molecular assays.

After confirmation of eligibility, patients will be randomly assigned in a 2:1 ratio to:

- Arm A: selpercatinib at a starting dose of 160 twice a day or
- Arm B: cabozantinib at a starting dose of 140 mg once daily, or vandetanib at a starting dose of 300 mg once daily. Patients cannot switch from cabozantinib to vandetanib or from vandetanib to cabozantinib during the study.

Treatment will continue until disease progression, unacceptable toxicity, or death. The treatment decision will be made by investigator assessment. Patients with disease progression per investigator assessment may continue treatment while awaiting blinded independent central review (BICR) confirmation of progression.

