 - In the ZETA study, the median PFS was 30.5 months for vandetanib-treated patients with newly diagnosed advanced MTC and patients with progression (Wells et al. 2012). A post hoc analysis provided median PFS results for two subgroups of patients that are similar to those enrolling in Study JZJB based on the presence of progressive disease within 12 months of enrollment. For those with both disease progression and symptoms in the prior 12 months, the median PFS was 21.4 months and for those with disease progression only in the prior 12 months, median PFS was not reached at a median follow-up of 95 months (Kreissl et al. 2020).

An initial assumption of 74 PFS events provides approximately 80% power to detect a hazard ratio (HR) of 0.5 using the logrank test and a 1-sided type I error of 2.5%. Given the historical data outlined above, a median PFS of 25 months is assumed for Arm B. HR of 0.5 corresponds to an improvement in median PFS from 25 months for Arm B to 50 months for Arm A. Approximately 250 patients will be enrolled based on these initial assumptions.

The sample size re-estimation will be based on PFS, so the sample size adjustment has the purpose of modifying the number of events. The number of patients will be adjusted to ensure the achievement of the required total number of events in an expeditious manner.

A re-estimation of the number of PFS events will be conducted only once, during the pre-specified interim efficacy analysis, based on the unblinded comparative results observed at this analysis. Based on prespecified criteria described in the Adaptive Design Charter the following scenarios are possible:

- the study will be declared positive due to overwhelming efficacy
- the study will continue without change to the final analysis (ie, the re-estimated total number of events will be equal to the initial planned total number of events)
- the re-estimated total number of events required for the final analysis will be determined and the study will continue to the final analysis.

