8.4.1.1.3. Main Analytical Approach

Since TFFS events include PFS events with additional events of treatment failure due to toxicity, TFFS is sufficiently powered as result of sample size determination based on PFS events.

Conditional on achieving a statistical significance for the primary endpoint of PFS, TFFS by BICR will be tested once at the time of the final analysis which is triggered by the PFS events, in a manner that will preserve the overall Type I error rate at the 1-sided significance level of 0.025 (see Section 8.8 Interim Analyses for details).

- If the study remains at the initial planned total number of PFS events and sample size, the TFFS will be compared between treatment arms using a stratified logrank test, stratified by the 2 randomization strata based on IWRS data: RET mutation (M918T vs. other) and intended control treatment (cabozantinib vs. vandetanib).
- If the total number of PFS events required for the final analysis increases after sample size re-estimation, the TFFS will be compared between treatment arms using the CHW test in a similar manner of the primary efficacy analysis:

Table JZJB.6. Defining the Values for Computing the CHW Test Statistic of TFFS

Quantity	Input Value or Derivation / Calculation
$Z_{TFFS,1}$	This is the stratified logrank test statistic comparing TFFS between treatment arms at the interim analysis. The interim analysis is triggered after approximately 56 PFS events have occurred (at 75% PFS information fraction).
$Z_{TFFS,2}$	This is the stratified logrank test statistic comparing TFFS between treatment arms at the final analysis.
$e_{TFFS,1}$	This is the observed number of TFFS events across both treatment arms at the interim analysis.
$e_{TFFS,2}$	This is the number of TFFS events across both treatment arms at the final analysis should the study remain at the initial planned 74 total number of PFS events. This number is projected to be 88 assuming a median TFFS of 20 months for Arm B (Wells et al. 2012) and HR of 0.5. $e_{TFFS,2} = 88$
$e_{TFFS,2}^*$	This is the observed number of TFFS events across both treatment arms at the final analysis.

Given the quantities defined in Table JZJB.6, the final CHW test statistic for the TFFS analysis can be written as:

$$Z_{TFFS,CHW} = \sqrt{\frac{e_{TFFS,1}}{e_{TFFS,2}}} Z_{TFFS,1} + \sqrt{\frac{e_{TFFS,2} - e_{TFFS,1}}{e_{TFFS,2}}} \left\{ \frac{\sqrt{e_{TFFS,2}^*} Z_{TFFS,2} - \sqrt{e_{TFFS,1}} Z_{TFFS,1}}{\sqrt{e_{TFFS,2}^* - e_{TFFS,1}}} \right\}$$

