Adverse event analyses will include summaries of the following:

- AEs, including severity and possible relationship to study drug
- SAEs, including possible relationship to study drug
- AEs leading to dose adjustments
- discontinuations from study treatment due to AEs or death
- time to any toxicity grade 3 or above
- **AEs of special interest (AESI)**: Categories of AESI will be identified as the understanding of the safety of selpercatinib increases. The final list of categories will be maintained at both compound and study level and reported in the Clinical Study Report.
- **Consolidated AEs** are composite AE terms consisting of synonymous PTs to allow meaningful interpretation of the AE data. The final list of consolidated AE categories and PTs will be maintained at both compound and study level and reported in the Clinical Study Report.

Deaths

- Summary of deaths (all deaths and deaths within 30 days of last dose of study drug) and their primary cause (study disease progression, AE, other)
- Listing of TEAEs leading to death.

Laboratory Abnormalities

The severity of laboratory results will be classified according to NCI-CTCAE. Treatment-emergent changes in laboratory values will be reported for the safety population. The laboratory toxicity by worst NCI-CTCAE grade and shifts in toxicity grading from baseline to the worst postbaseline grade will be summarized.

Shift to low/high tables will include the number and percentage of patients within each baseline category (baseline value is low, normal, high, or missing) versus each postbaseline category (worst value is low, normal, high, or missing) by treatment arm.

RET Testing Results Concordance

The concordance between RET testing results based on local laboratory tests and centrally assessed results will be evaluated. Details regarding analyses involving centrally assessed RET testing results will be described in a separate diagnostics SAP.

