8.7.5. Health Care Resource Utilization

Summaries of hospitalizations, emergency room visits, granulocyte-colony stimulating factor (G-CSF) use, transfusions, and analgesic use will be reported descriptively for each treatment arm. Due to potential differential treatment durations, hospitalizations and emergency room visits per on-treatment month will also be reported by arm.

Duration of hospital stays and average number of emergency room visits will be reported by treatment arm.

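### AE and SAE tables give only crude percentages by arm although treatment is expected to last longer on selpercatinib; exposure-adjusted rates should be prespecified beside them

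*SAP*

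**What the plan says.** Safety relative to the control drugs is a secondary objective, measured by incidence and severity of TEAEs, SAEs, deaths and laboratory abnormalities (SAP Section 4.1).

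The planned summary is a count of patients. Protocol Section 9.4.4 asks for number and percent with TEAEs. SAP Section 8.4.2 tabulates them by System Organ Class and, within class, by decreasing frequency of preferred term. Its list of AE summaries begins with "AEs, including severity and possible relationship to study drug" and goes on to SAEs, dose adjustments and discontinuations. No item uses patient-time as a denominator. One item is time-based: time to a toxicity of grade 3 or higher, with no method or censoring rule.

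TEAEs are counted until 30 days after core-period treatment ends. On treatment length, SAP Section 4.2 says: "Treatment will continue until disease progression, unacceptable toxicity, or death". Events after crossover are summarized separately (SAP Section 8.5).

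For health care use, SAP Section 8.7.5 does allow for unequal exposure: "Due to potential differential treatment durations, hospitalizations and emergency room visits per on-treatment month will also be reported by arm". The FACT-GP5 tolerability endpoint is also divided by each patient's duration of therapy (SAP Section 8.4.1.2.2).

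**The concern.** The observation window for AEs is tied to time on treatment, and the plan expects that time to differ between arms. Protocol Section 2.3 also expects few AE discontinuations on selpercatinib compared with the control drugs. A crude percentage then mixes two things: how toxic the drug is per unit of time, and how long patients stayed on it. The longer-treated arm accumulates more patients with at least one event even when the underlying rates are equal.

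What is at stake is how the safety comparison reads. An equal rate would look like an excess on selpercatinib, and a real advantage could be hidden. The SAP acknowledges the problem for hospitalizations and emergency visits but leaves it unaddressed for the named secondary safety endpoint. The distortion grows with follow-up, so it matters more if the event target is raised from 74 towards 284.

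**Working it through.** **The plan's own figure.** The 25 and 50 month medians come from the sample size section (SAP Section 6): "An initial assumption of 74 PFS events provides approximately 80% power to detect a hazard ratio (HR) of 0.5", and "HR of 0.5 corresponds to an improvement in median PFS from 25 months for Arm B to 50 months for Arm A". With 2:1 allocation and one-sided 2.5%, the Schoenfeld formula gives (1.960 + 0.842)² / [(2/3)(1/3)(ln 0.5)²] = 7.849 / 0.1068 = 73.5, so 74 events; power at 74 is 80.3%. The figure reproduces. The documents state no AE rate.

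**Inputs from the documents.** 250 patients; 2:1; PFS medians 50 (A) and 25 (B) months; a control TFFS median of 20 months (SAP Section 8.4.1.1.3: "This number is projected to be 88 assuming a median TFFS of 20 months for Arm B"), hence 40 months for A at HR 0.5; 6-year cap.

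**Assumptions not in the documents.** Time on treatment is exponential, with PFS or TFFS as its proxy. Accrual is uniform over 24–36 months. The AE hazard λ is constant and equal in both arms, at 0.01 or 0.03 per month.

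**Formulas.** With μ = ln 2 / median and follow-up F:
- mean exposure = (1 − e^(−μF)) / μ
- crude incidence = λ/(λ+μ) × (1 − e^(−(λ+μ)F))

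Both are averaged over staggered entry.

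**Worked example at one fixed follow-up.** λ = 0.2 per patient-year = 0.01667 per month, F = 24 months.
- B: μ = 0.02773; 0.3754 × (1 − e^(−1.065)) = 0.3754 × 0.655 = 24.6%
- A: μ = 0.01386; 0.5459 × (1 − e^(−0.733)) = 0.5459 × 0.519 = 28.4%

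The true rate ratio is 1.00, but the crude ratio is 1.15.

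**With staggered entry, 250 patients.** Solving for 74 expected PFS events puts the cut at 31.9 months (24 months' accrual) to 38.5 months (36 months' accrual) from first entry. The incidence columns use the PFS medians and show A versus B; the exposure column covers both pairs of medians.

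| Cut | Exposure ratio A:B | λ = 0.01/month | λ = 0.03/month |
|---|---|---|---|
| 74 PFS events | 1.15–1.21 | 15.4–15.5% vs 13.3–13.6% | 37.6–38.5% vs 33.0–34.1% |
| 72 months | 1.36–1.48 | 30.0–31.8% vs 22.8–23.7% | 61.3–63.2% vs 49.2–50.2% |

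The excess is about 2 and 4–5 points at 74 events, and about 7–8 and 12–13 points at the cap. These figures leave out the 30-day tail. With the tail included, at rates of 0.1–0.5 per patient-year, 24–36 months' accrual and cuts at 30–48 months, the crude ratio is 1.10–1.24.

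**In reverse.** With control at 0.2 per patient-year and 24–36 months' follow-up, the arms show equal crude incidence when the selpercatinib rate is 0.74–0.84 of control.

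**Early-onset events.** Take an illustrative hazard of 0.15 per month for 3 months and 0.015 after that, so cumulative hazard is 0.15·min(t,3) + 0.015·max(t−3,0). Near 74 events this gives about 47% versus 45% on PFS medians, and 47% versus 44% on TFFS medians: a gap of 2–3 points.

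**The case against.** Number and percent of patients with TEAEs is a standard descriptive summary, and nothing in it is wrong in itself. No between-arm test of AEs is planned. The AE list is introduced as what the summaries will include, so it is open-ended, and SAP Section 8.1 allows further exploratory analyses. The time-to-grade-3 item and the duration-scaled FACT-GP5 endpoint already bring time into the toxicity assessment. Exposure is summarized by arm (SAP Section 8.6.1), and the registry tables give event counts and patients at risk (SAP Section 8.7.9). The distortion runs against the sponsor's own drug, so it is conservative for a safety claim. Finally, a rate per patient-year also assumes a constant hazard: for early-onset toxicity it dilutes the rate in the longer-treated arm and would favour selpercatinib.

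Most of this stands and limits the point. It does not remove it. The time-based item is a single composite without a stated method, and it does not cover SAEs, individual terms or lower grades. FACT-GP5 measures reported bother, not AE incidence. Average exposure does not yield first-event rates by term. Permission to add analyses is not prespecification, which carries weight in an open-label trial. The early-onset argument affects the form of the fix.

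A reader might infer that the plan ignores treatment duration altogether, or that its safety conclusions are invalid. The documents support neither: duration is handled in part, and crude tables are legitimate when read beside exposure.

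**Conclusion.** The point holds as a minor gap. The AE and SAE tables have no time-adjusted counterpart, although the plan expects unequal exposure and adjusts for it elsewhere. At equal constant hazards the selpercatinib column would be inflated by roughly 2–5 points near 74 PFS events and 7–13 points at the 6-year cap. Those sizes rest on the assumed AE hazards, accrual, exponential treatment time and PFS as a proxy for time on treatment; for events concentrated in the first cycles the gap near 74 events is 2–3 points. A sample size increase towards 400 was not modelled.

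It would be wrong to read this as a threat to the primary result: PFS, TFFS and comparative tolerability are the error-controlled endpoints, and none uses AE percentages. Nor is it a bias in favour of selpercatinib, since under the design assumptions it runs the other way.

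**What to change.** In SAP Section 8.4.2, keep the crude tables and prespecify beside them, by arm, first events and all events per 100 patient-years for any-grade, grade 3 or higher, serious and discontinuation AEs. Use the on-treatment plus 30-day window as person-time, stopping at the first event for the first-event rate. State the duration formula for each drug; the one printed in SAP Section 8.6.1 names only selpercatinib.

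Because these rates dilute early-onset events in the longer-treated arm, also give cumulative incidence at fixed times for grade 3 or higher AEs and for SAEs, with death and treatment discontinuation for other reasons as competing events. Include an early time point: this measure still depends on how long patients stay on treatment, but at 12 months the ratio produced by unequal duration alone is only 1.08–1.10 (rates of 0.05–0.5 per patient-year). SAP Section 8.5 already uses cumulative incidence for time to new therapy. State the method and censoring rule for the time-to-grade-3 item as well.

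The cost is extra table columns and a footnote on the constant-hazard assumption. The data are already collected.

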8.5. Tertiary/Exploratory Endpoint Analyses

Calcitonin response rate

Calcitonin response rate is defined as percentage of patients who had a decline from baseline in the calcitonin level of at least 50% maintained for at least 4 weeks. Calcitonin response rate will be compared between Arm A and Arm B using a CMH test stratified by the randomization strata.

CEA response rate

Carcinoembryonic antigen (CEA) response rate is defined as percentage of patients who had a decline from baseline in the CEA level of at least 50% maintained for at least 4 weeks.

Carcinoembryonic antigen response rate will be compared between Arm A and Arm B using a CMH test stratified by the randomization strata.

PROs

Further details of planned analysis of PROs will be provided in a separate SAP.

PFS/ORR/DOR/DCR After Crossover

Progression-free survival after crossover in crossover population is defined as the time from start of selpercatinib treatment until the occurrence of disease progression or death from any cause. Patients known to be alive and without disease progression will be censored at the time of the last adequate tumor assessment.

Duration of response is defined as the time from the date that measurement criteria for CR or PR with respect to the crossover baseline tumor assessment are first met until the first date that disease is recurrent or documented disease progression is observed, or the date of death from any cause in the absence of documented disease progression or recurrence during crossover period.

Survival curve, the median, and rates at various time points with 95% CI will be estimated using the Kaplan-Meier method (Kaplan and Meier 1958).

Overall response rate after crossover is defined as the number of patients who achieve a BOR of CR or PR with respect to the crossover baseline tumor assessment, divided by the total number of patients in crossover population. Disease control rate after crossover is defined as the number of patients who achieve a BOR of CR, PR or stable disease (SD) lasting 16 or more weeks, with respect to the crossover baseline tumor assessment, divided by the total number of patients in crossover population. The ORR and DCR after crossover with 95% CI will be summarized.

Additional exploratory analyses to compare efficacy endpoints prior versus post crossover intra-patient may be performed as deemed appropriate.

TEAE and Lab Abnormalities After Crossover

Treatment-emergent adverse events (TEAEs) after crossover are events that first occurred or worsened in severity after crossover baseline and up to 30 days after crossover treatment discontinuation. Treatment-emergent adverse events will be summarized by System Organ Class (SOC) and by decreasing frequency of PT within SOC.

The severity of laboratory results after crossover will be classified according to NCI-CTCAE. Treatment-emergent changes in laboratory values after crossover will be reported for the crossover population. The laboratory toxicity by worst NCI-CTCAE grade and shifts in toxicity grading from crossover baseline to the worst post crossover baseline grade will be summarized.

Time to Initiation of New Anticancer Therapy

Time to initiation of new anticancer therapy is defined as the time from randomization to documentation in the case report forms of a new local (eg surgery, radiation) or systemic anticancer treatment administered to the patient.

Death is considered as a competing event. To account for the competing risk from death, the probability of initiation of new anticancer therapy will be estimated by treatment arm using a cumulative-incidence function (subdistribution function). A plot of the estimated cumulative-incidence functions will be displayed for each treatment arm. Time to initiation of new anticancer therapy will be compared between treatment arms using a stratified logrank test, computed on the basis of cause-specific hazard functions. The corresponding cause-specific HRs will be estimated using a stratified Cox regression model.

Biomarkers

Biomarkers assessed from blood or tissue samples and their relationship with clinical outcomes will be analyzed according to a separate translational research analysis plan.

8.6. (Other) Safety Analyses

8.6.1. Extent of Exposure

The number of cycles received, dose reductions, dose withholding, and dose intensity for each drug will be summarized for all treated patients by treatment arm. The exposure derivations are provided below:

- Duration of therapy (weeks) = (date of last dose of selpercatinib - date of first dose of selpercatinib + 1) ÷ 7
- Cumulative dose (mg) = sum of all doses
- Dose intensity (mg/week) = (cumulative dose) ÷ (duration of therapy)
- Planned dose intensity (mg/week) = daily dose (mg) * 7
- Relative dose intensity (%) = (dose intensity / planned dose intensity) * 100

All analyses of selpercatinib exposure will be performed for the study treatment period for patients randomly assigned to Arm A as well as for the crossover period for patients assigned to Arm B who crossover to selpercatinib after disease progression. All analyses of cabozantinib and vandetanib exposure will be performed for the study treatment period for patients randomly assigned to Arm B and stratified to receive cabozantinib or vandetanib respectively.

8.6.1.1. Treatment Compliance

Compliance for each drug will be assessed as the proportion of treatment that is actually taken, relative to what is expected, after accounting for protocol-defined dose adjustments. Study treatment taken will be derived from the difference between the total number of capsules dispensed and returned over the course of the patient's treatment. A patient will be considered noncompliant if he or she takes <75% or ≥125% of the planned doses for the duration of the study treatment.

Summaries will be provided for the study treatment period for Arm A and Arm B patients as well as for the crossover period for patients assigned to Arm B who crossover to selpercatinib after disease progression.

